Keys: AR=androgen receptor; β-hCG=beta human chorionic gonadotropin; C1D1=Cycle 1 Day 1; CT=computed tomography; CTC=circulating tumor cell; E2=estradiol; ctDNA/RNA=circulating tumor DNA/RNA; ECG=electrocardiogram; ECOG-PS=Eastern Cooperative Oncology Group performance status; eCRF=electronic case report form; EOT=end-of-treatment; FDG-PET=fluorodeoxyglucose-positron emission tomography; FFPE=formalin-fixed paraffin-embedded; FSH=follicle stimulating hormone; GnRH=gonadotropin-releasing hormone; HER2=human epidermal growth factor receptor 2; HDL=high-density lipoprotein; ICF=informed consent form; LDL=low-density lipoprotein; LH=luteinizing hormone; MRI=magnetic resonance imaging; PK=pharmacokinetic(s); PSA=prostate-specific antigen; q3 cycles=every 3 cycles; ULN=upper limit of normal; T3=triiodothyronine; T4=free thyroxine; TSH=thyroid-stimulating hormone.

Footnotes:

- a. Must sign the ICF before first study-related activity.

- b. Every effort should be made to document radiographic progression, even after discontinuation of treatment for safety or tolerability reasons (eg, AE) but prior to subsequent therapy.
- c. If a participant discontinues study intervention for safety or tolerability reasons (eg, AE), radiographic evaluations must be continued until disease progression but prior to subsequent therapy according to the same schedule as the one of prediscontinuation (every 2 cycles or every 3 cycles beginning at Cycle 13 from Cycle 1 Day 1) unless (s)he withdraws consent for follow-up.
- d. Locally performed. For fasting laboratory assessments, if the participant has not fasted before the visit, the visit may proceed, but the participant must return within 72 hours in a fasted state to provide the necessary sample(s) for the assessments.
- e. Follow-up for survival will continue until death, withdrawal of consent, lost to follow-up or until the end of the study. Deaths regardless of causality will be reported in the eCRF. Serious adverse events that occur after 30 days following the last drug administration thought to be related to study intervention will be collected and reported via the Serious Adverse Event form within 24 hours of discovery or notification of the event and documented (refer to Section 8.3.1).
- f. Fasting state is defined as 8 hours without food or drink, with the exception of water.
- g. A blood sample will be collected at any time between 0.5 to 4 hours after the apalutamide administration.

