8.3. Adverse Events and Serious Adverse Events

Timely, accurate, and complete reporting and analysis of safety information from clinical studies are crucial for the protection of participants, investigators, and the sponsor, and are mandated by regulatory agencies worldwide. The sponsor has established Standard Operating Procedures in conformity with regulatory requirements worldwide to ensure appropriate reporting of safety information; all clinical studies conducted by the sponsor or its affiliates will be conducted in accordance with those procedures.

Adverse events will be reported by the participant (or, when appropriate, by a caregiver, surrogate, or the participant's legally acceptable representative) for the duration of the study.

For further details on AEs and SAEs (Definitions and Classifications; Attribution Definitions; Severity Criteria; Special Reporting Situations; Procedures) as well as product quality complaints (PQCs), refer to Section 10.4, Appendix 4, Adverse Events: Definitions and Procedures for Recording, Evaluating, Follow-up, and Reporting.

8.3.1. Time Period and Frequency for Collecting Adverse Event and Serious Adverse Event Information

All Adverse Events

All AEs and special reporting situations, whether serious or nonserious, will be reported from the time a signed and dated ICF is obtained until 30 days after the last dose of study intervention. Serious adverse events (SAEs), including those spontaneously reported to the investigator within 30 days after the last dose of study intervention, must be reported using the Serious Adverse Event Form. The sponsor will evaluate any safety information that is spontaneously reported by an investigator beyond the time frame specified in the protocol.

Serious Adverse Events

All SAEs occurring during the study must be reported to the appropriate sponsor contact person by study-site personnel within 24 hours of their knowledge of the event. Also, SAEs that occur after 30 days following the last intervention administration and are considered to be related to the study intervention will be collected and reported to the appropriate sponsor contact person.

Information regarding SAEs will be transmitted to the sponsor using the Serious Adverse Event Form, which must be completed and signed by a physician from the study site, and transmitted to the sponsor within 24 hours. The initial and follow-up reports of an SAE should be made according to the safety monitoring plan.

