9.4.3. Safety Analyses

All safety analyses will be made on the treated population.

Adverse Events

The verbatim terms used in the eCRF by investigators to identify AEs will be coded using the Medical Dictionary for Regulatory Activities (MedDRA). Toxicities will be graded for severity according to NCI-CTCAE, version 5.0. Any AE occurring at or after the initial administration of study intervention through the day of last dose plus 30 days is considered to be treatment-emergent. All reported AEs will be included in the analysis. For each AE, the percentage of participants who experience at least 1 occurrence of the given event will be summarized.

Clinical Laboratory Tests

Laboratory data will be summarized by type of laboratory test. Descriptive statistics will be calculated for all laboratory analyte at baseline and at selected scheduled timepoints. Parameters with predefined NCI-CTCAE toxicity grades will be summarized. Change from baseline to the worst toxicity grade experienced by the participants during the study will be provided as shift tables.

Vital Signs

Descriptive statistics of blood pressure (systolic and diastolic) values and changes from baseline will be summarized.

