#### 2.4. Imputation Rules for Missing AE Date/Time of Onset/Resolution

Treatment-emergent adverse events (TEAEs) for the treatment phase are those events with an onset date/time on or after the start of study intervention through the day of last dose plus 30 days is considered to be treatment -emergent.

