### **6.1. Adverse Events**

The verbatim terms used in the CRF by investigators to identify adverse events (AE) will be coded using the Medical Dictionary for Regulatory Activities (MedDRA). Any AE occurring at or after the initial administration of study agent through the day of last dose plus 30 days is considered to be treatment emergent. If the event occurs on the day of the initial administration of study agent, and either event time or time of administration are missing, then the event will be assumed to be treatment emergent. If the event date is recorded as partial or completely missing, then the event will be considered to be treatment emergent unless it is known to be prior to the first administration of study agent based on partial onset date or resolution date. All reported treatment-emergent adverse events will be included in the analysis. For each adverse event, the number and percentage of subjects who experience at least 1 occurrence of the given event will be summarized.

A summary for tables and listings is shown in [Table 7](#):

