**Table 7: Tables and Listings to be Developed**

Analysis	Sorted By	Table	Drug-Related TEAE Table	Listing
Overall summary		✓		
TEAEs	SOC+ PT;	✓	✓	✓
	SOC+PT+toxicity grade;	✓	✓	
Serious TEAEs	SOC+ PT;	✓	✓	
	SOC+PT+toxicity grade;	✓	✓	✓
Grade 3 or higher TEAE	SOC+PT	✓	✓	
Grade 3 or higher serious TEAE	SOC+PT	✓		
TEAEs leading to treatment discontinuation	SOC+PT+Toxicity	✓	✓	✓
TEAEs leading to death	SOC+PT	✓		✓
TEAEs leading to dose reduction	SOC+PT	✓		
TEAEs leading to treatment interruption	SOC+PT	✓		
AEs of special interest	SOC+PT	✓		
	SOC+PT+Toxicity	✓		
AEs of clinical interest	SOC+PT	✓		
Deaths	Reason for death	✓		
TEAEs by time period	SOC + PT	✓		

For TEAEs by relationship to treatment, TEAEs leading to dose reduction, tables will be provided separately for apalutamide and goserelin.

TEAEs by time period will be provided for TEAE starting time <16 Weeks, 16<= - <32 Weeks, =>32 Weeks and total.

Female safety records for exploratory endpoints will be listed with other lab and AEs. No particular analysis will be done for them.

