## 6.4. Death

A summary of the number of deaths will be provided by time period (on-study vs during follow-up), along with the primary cause of death. Frequencies of on-study deaths due to study treatment-related adverse events will also be reported. A death is study intervention -related death if the primary cause is a drug related AE.

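### Drug-related SAEs starting more than 30 days after the last dose are collected, but SAP 6.1 limits the analysis to treatment-emergent events, so no serious, drug-related or listed TEAE output includes them

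*SAP*

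**What the plan says.** **Collection.** Protocol 8.3.1 ends general AE reporting 30 days after the last dose but makes one exception: "SAEs that occur after 30 days following the last intervention administration and are considered to be related to the study intervention will be collected". Footnote e of the Schedule of Activities (Protocol 1.3) repeats it: "Serious adverse events that occur after 30 days following the last drug administration thought to be related to study intervention will be collected". Neither text sets an end date.

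**Definition.** SAP 6.1 gives the window for treatment-emergent events: "Any AE occurring at or after the initial administration of study agent through the day of last dose plus 30 days is considered" such an event. SAP 2.4 uses the same window: "onset date/time on or after the start of study intervention through the day of last dose plus 30 days". Neither section has a clause for later events judged related. Protocol 9.4.3 defines treatment-emergent the same way.

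**Scope of analysis.** Protocol 9.4.3 says "All reported AEs will be included in the analysis". SAP 6.1 says "All reported treatment-emergent adverse events will be included in the analysis".

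**Outputs.** In SAP Table 7 the column for related events is headed "Drug-Related TEAE Table". Four rows carry a listing: TEAEs, serious TEAEs, TEAEs leading to discontinuation, and TEAEs leading to death.

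**Deaths.** SAP 6.4 summarises deaths by period (on-study or follow-up) with primary cause, then adds: "Frequencies of on-study deaths due to study treatment-related adverse events will also be reported".

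**The concern.** The protocol stops collecting AEs in general 30 days after the last dose and keeps collecting one kind only: serious events that the investigator attributes to treatment. The SAP then provides no table or listing meant for them. The omission runs in one direction, since leaving out a related SAE can only make the reported profile look better.

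Safety profile is a secondary endpoint (Protocol 3), and an acceptable safety profile is part of the hypothesis in Protocol 9.1. Protocol 2.2 states that the safety of apalutamide has not been studied in women. In a study of about 24 people, a single late related SAE is information a reader of the study report would expect to find.

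**Working it through.** The plan states no figure on this point to reproduce. The check traces one event through the texts.

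**Trace.** Take an SAE judged related, with a complete onset date 31 or more days after the last dose.

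1. Is it collected? Yes (Protocol 8.3.1; Schedule of Activities, footnote e).
2. Is it treatment-emergent? No. Its onset is outside the window in SAP 2.4 and 6.1, and relatedness does not bring it in.
3. Is it in the analysis? Yes under Protocol 9.4.3, no under SAP 6.1. Neither SAP amendment mentions this narrowing.
4. Is it in a SAP Table 7 output?

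| Output | Late related SAE included? |
|---|---|
| TEAE, serious TEAE and Grade 3 or higher TEAE tables | No |
| Drug-related column | No; it is limited to TEAEs |
| TEAEs leading to discontinuation, dose reduction, interruption or death; TEAEs by time period | No |
| The four listings | No; all are on TEAE rows |
| Overall summary | Unlabelled here; Table 2 titles the interim version as TEAEs |
| AEs of special interest and of clinical interest | Ambiguous: not labelled TEAE here or in SAP 6.2 and 6.3, but SAP 6.1 and the interim title in Table 2 (special interest only) point to TEAEs; neither row has a listing |
| Listing of female safety records | Ambiguous: no stated limit to TEAEs |
| Deaths by reason | Only if fatal |

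5. If it is fatal, is it counted as a treatment-related death? SAP 6.4 defines such a death by its cause, with no time limit, but reports the frequency for on-study deaths only. A death classed as follow-up is shown by cause and not counted as treatment-related.

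**One exception.** Under SAP 6.1, partial or missing dates default to treatment-emergent unless the event is known to precede the first dose. A late event with an incomplete date could therefore be counted while a fully dated one is not.

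**Size.** Input: 24 treated participants, an assumption based on the target of approximately 24 in Protocol 1.1. One newly counted participant moves a rate by 1/24 = 4.2 percentage points. Clopper-Pearson 95% limits:

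- 0/24: the upper limit is 1 − 0.025^(1/24) = 14.2%, so 0% (0 to 14.2%).
- 1/24: the lower limit is 1 − 0.975^(1/24) = 0.1% and the upper limit is 21.1%, so 4.2% (0.1 to 21.1%).

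The shift applies only if that participant is not already counted in the same row. With more than 24 treated it is smaller.

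**The case against.** The strongest reply is that the gap is narrow. The 30-day window is the protocol's own definition, so the SAP does not depart from it there; the two documents differ only in the sentence on scope. Late related SAEs still go to the sponsor within 24 hours and fall under the regulatory reporting duties in Protocol 8.3.3, so they are absent from planned tables and not from safety oversight. Late deaths of any cause are also collected and tabulated. Efficacy and futility rest solely on ORR, so no trial decision changes. All of this stands, and it limits the importance of the point. It does not supply an output for the events.

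Three stronger readings are tempting, and the documents do not support them.

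- A reader might infer that these events vanish from every AE summary and listing. The special-interest and clinical-interest rows and the female listing leave room for some of them, and fatal ones appear among the deaths.
- A reader might infer that the treatment-emergent definition should be widened to any related event at any time. After day 30 only related serious events are collected, so the Table 7 rows would then mix complete collection up to day 30 with selective collection afterwards, and Protocol 9.4.3 would have to be amended.
- A reader might argue from drug exposure that 30 days is too short. The 7-day half-life in Protocol 2.2 gives 2^(−30/7) = 5.1% remaining at day 30. That half-life is from single doses in healthy men. The same section gives about 5-fold accumulation on daily dosing. In a one-compartment model (assumed), 1/(1 − r) = 5 gives r = 0.8 per day and 0.8^30 = 0.12% remaining. The text thus supports anything from about 0.1% to 5%, and the period of at least 35 days in Protocol 8.4 concerns overdose monitoring. The point does not rest on exposure.

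**Conclusion.** The point holds as a mismatch between collection and analysis, and between Protocol 9.4.3 and SAP 6.1. If the SAP is followed as written, a fully dated related SAE with onset after last dose plus 30 days is left out of the TEAE, serious-TEAE and drug-related TEAE tables and all four Table 7 listings. If it is fatal, it is also left out of the treatment-related death frequency, provided that a death after day 30 is classed as follow-up; SAP 6.4 does not define the boundary.

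The number of such events cannot be known from the documents and may be zero. Each newly counted participant would move a rate by about 4 percentage points if about 24 are treated, always toward a less favourable profile. The omission is worth closing because it runs one way and affects a secondary endpoint. It does not affect the primary test.

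**What to change.** - **SAP 2.4 and 6.1:** keep the 30-day treatment-emergent window. Reword the scope sentence in 6.1 to agree with Protocol 9.4.3: TEAEs go into the main tables, and reported events outside the window have a stated place. Because AEs are collected from consent, the wording should also say where events before the first dose are shown.
- **SAP Table 7:** add one table and one listing of SAEs considered related with onset after last dose plus 30 days, by SOC, PT, toxicity grade and study agent. State whether the special-interest and clinical-interest rows and the female listing are limited to TEAEs.
- **SAP 6.4:** report treatment-related deaths for both the on-study and the follow-up period, and define the boundary between them.

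The cost is a short SAP amendment and minor programming on data already collected, with no protocol amendment. The downside is that reported safety may look slightly less favourable. Late events should stay in their own table, because collection after day 30 is selective.

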**Table 7: Tables and Listings to be Developed**

Analysis	Sorted By	Table	Drug-Related TEAE Table	Listing
Overall summary		✓		
TEAEs	SOC+ PT;	✓	✓	✓
	SOC+PT+toxicity grade;	✓	✓	
Serious TEAEs	SOC+ PT;	✓	✓	
	SOC+PT+toxicity grade;	✓	✓	✓
Grade 3 or higher TEAE	SOC+PT	✓	✓	
Grade 3 or higher serious TEAE	SOC+PT	✓		
TEAEs leading to treatment discontinuation	SOC+PT+Toxicity	✓	✓	✓
TEAEs leading to death	SOC+PT	✓		✓
TEAEs leading to dose reduction	SOC+PT	✓		
TEAEs leading to treatment interruption	SOC+PT	✓		
AEs of special interest	SOC+PT	✓		
	SOC+PT+Toxicity	✓		
AEs of clinical interest	SOC+PT	✓		
Deaths	Reason for death	✓		
TEAEs by time period	SOC + PT	✓		

For TEAEs by relationship to treatment, TEAEs leading to dose reduction, tables will be provided separately for apalutamide and goserelin.

TEAEs by time period will be provided for TEAE starting time <16 Weeks, 16<= - <32 Weeks, =>32 Weeks and total.

Female safety records for exploratory endpoints will be listed with other lab and AEs. No particular analysis will be done for them.

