4. STUDY DESIGN

4.1. Overall Design

This is an open-label, single-arm, multicenter, Phase 2 study to evaluate the efficacy and safety of apalutamide in combination with a GnRH agonist in participants with AR expressing locally advanced or recurrent/metastatic SGC.

A target of 24 participants will be included in this study and receive apalutamide and a GnRH agonist.

The study will consist of a screening phase, a treatment phase, and a follow-up phase. The study is anticipated to end approximately 42 months after the first participant is consented.

The study will be conducted in an outpatient setting and a treatment cycle is defined as 28 days. Study intervention will continue until disease progression, unacceptable toxicity, death, or the end of the study. Study intervention will be discontinued if a participant meets any of criteria described in Section 7.1, Discontinuation of Study Intervention.

After discontinuing study intervention, participants will be contacted every 6 months (refer to the SoA in Section 1.3) until death or the end of the study.

Participants will be monitored for safety starting from the signing of informed consent until 30 days after the last dose of study intervention. Adverse events including laboratory AEs will be graded and summarized using version 5.0 of the National Cancer Institute-Common Terminology Criteria for AEs (NCI-CTCAE). Dose modifications will be made as required according to dose modification rules (Section 6.6). An independent central radiology review will be used to reduce potential bias during data collection and evaluation of the primary endpoint of ORR and secondary endpoints including PFS (Section 9).

A diagram of the study design is provided in Section 1.2, Schema.

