### **1.2. Trial Design**

This is an open-label, single-arm, multicenter, Phase 2 study to evaluate the efficacy and safety of apalutamide in combination with a GnRH agonist in participants with AR expressing locally advanced or recurrent/metastatic SGC.

The study will consist of a screening phase, a treatment phase, and a follow-up phase. Study intervention will continue until disease progression, unacceptable toxicity, death, or the end of the study. Study intervention will be discontinued if a participant meets any of criteria for discontinuation of study intervention. Dose modifications will be made as required according to dose modification rules. An independent central radiology review (ICRR) will be used to reduce potential bias during data collection and evaluation of the primary endpoint of overall response and secondary endpoints including progression-free survival (PFS).

An interim analysis will be performed when 12 response evaluable participants are observed for at least 24 weeks after the initiation of study intervention. Final analysis will be conducted when 24 response evaluable participants are observed for at least 24 weeks.

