## 2.2. Analysis Set

For purposes of analysis, the following populations are defined:

Population	Description
Enrolled	All participants who sign the ICF.
Treated	All participants who receive at least 1 dose of study intervention. This population will be used for all analyses including efficacy, safety, and biomarker unless otherwise specified.
Response evaluable	All participants who are AR positive by local test and who are confirmed evaluable by an independent central radiology review (ICRR). Also, all participants who receive at least 1 dose of study intervention and who have at least 1 postbaseline disease assessment or died due to disease progression before the first postbaseline disease assessment. This population will be considered for primary efficacy analysis.  Note: Confirmed evaluable by an independent central radiology review means the participant had at least one target lesion confirmed by ICRR.
Pharmacokinetic	All participants with at least 1 apalutamide and/or N-desmethyl apalutamide concentration data after the first study intervention administration.

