## **6. SAFETY**

All safety analyses will be made on the treated population.

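### The table of TEAEs by onset period has no stated at-risk denominator; on the default reading its later percentages understate risk among those still exposed

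*SAP*

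**What the plan says.** SAP 6 sets one analysis set for safety: "All safety analyses will be made on the treated population". Protocol 9.4.3 says the same. SAP 2.2 defines that population as "All participants who receive at least 1 dose of study intervention", so it does not shrink as participants stop treatment.

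SAP 6.1 gives the statistic. For each adverse event, "the number and percentage of subjects who experience at least 1 occurrence of the given event will be summarized". An event counts if it starts from first dose "through the day of last dose plus 30 days is considered to be treatment emergent".

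Table 7 includes a TEAE table by time period, sorted by system organ class and preferred term. The text beneath it says that "TEAEs by time period will be provided for TEAE starting time" in three periods (<16, 16 to <32 and ≥32 weeks) and in total.

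No section says what the percentage in each period is divided by. No number at risk per period and no rate per unit of exposure is planned. Treatment duration is summarised on its own in SAP 4.4.

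**The concern.** A table split by onset time will be read for when toxicity occurs. A participant whose treatment-emergent window closed before week 32 cannot contribute an event to the last column, yet remains in its denominator if all treated participants are used. SAP 1.2 gives the main route out: "Study intervention will continue until disease progression, unacceptable toxicity, death, or the end of the study". A second route is the data cutoff. The final analysis is triggered at 24 weeks of evaluation (SAP 3), so a late entrant may still be on treatment then without having reached week 32.

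A low late percentage could therefore reflect few people at risk rather than low risk. The last period raises a separate problem: it is open-ended, so it may collect far more time per participant than the two 16-week periods before it. The printed columns would mix attrition, unequal length and risk.

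**Working it through.** The plan gives no figure for this table, so there is none to reproduce. The check is an identity, followed by illustrations under stated assumptions.

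**Inputs from the documents**
- Target size: "A target of 24 participants will be included in this study and receive apalutamide and a GnRH agonist" (Protocol 4.1).
- Periods: <16, 16 to <32 and ≥32 weeks (SAP 6.1).
- Treatment-emergent window: first dose to last dose plus 30 days (SAP 6.1).
- Anticipated study length: about 42 months (Protocol 4.1).

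**Assumed, because the documents are silent:** the share still at risk at weeks 16 and 32, and the risk in each period.

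**Step 1: the identity.** Let N be all treated, n the number at risk at the start of a period, and x the participants with an onset in it. Then

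printed % = x/N = (x/n) × (n/N).

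The printed figure is the at-risk percentage times the share at risk. Whenever n < N and x > 0, it is the smaller of the two.

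**Step 2: a true 20% risk in each period among those at risk**

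| At risk at week 16 / 32 | <16 wk | 16 to <32 wk | ≥32 wk |
|---|---|---|---|
| 90% / 75% | 20% | 0.20 × 0.90 = 18% | 0.20 × 0.75 = 15% |
| 80% / 60% | 20% | 0.20 × 0.80 = 16% | 0.20 × 0.60 = 12% |
| 70% / 50% | 20% | 0.20 × 0.70 = 14% | 0.20 × 0.50 = 10% |
| 60% / 40% | 20% | 0.20 × 0.60 = 12% | 0.20 × 0.40 = 8% |

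An at-risk denominator gives 20% in every cell.

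**Step 3: in counts.** Three participants with an onset at ≥32 weeks print as 3/24 = 12.5%. Against 18, 14, 12 or 10 at risk, the same three are 16.7%, 21.4%, 25.0% or 30.0%.

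**Step 4: must the columns fall?** Step 2 holds risk per period equal, which disregards the length of the last period. Instead take a constant onset hazard h = −ln(0.8)/16 per week (20% per 16 weeks without dropout) and a constant discontinuation hazard d = ln 2 / median weeks on treatment. The chance of an onset on treatment within L weeks, among those at risk at the start, is

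h/(h+d) × [1 − exp(−(h+d)L)].

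The all-treated figure multiplies this by exp(−d × period start). For the last period, L = 42 × 4.348 − 32 ≈ 150.6 weeks. This is a generous bound, since only the earliest participants could have it. The 30-day tail is left out for simplicity.

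| Assumed median on treatment | All treated: <16 / 16 to <32 / ≥32 wk | At risk: ≥32 wk |
|---|---|---|
| 24 weeks | 16.2 / 10.2 / 12.9% | 32.5% |
| 52 weeks | 18.1 / 14.6 / 32.8% | 50.3% |

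The hazard is constant throughout, yet the all-treated columns dip and then rise, and with a 52-week median the last is the highest. The last column still understates the at-risk proportion in both cases. The at-risk proportion is itself inflated relative to the earlier periods by the longer window, so changing the denominator alone does not make the periods comparable. A rate per person-time is needed as well.

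**The case against.** The case on the other side has four parts.

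**The denominator is not specified.** A reader might infer that the SAP fixes all treated participants as the divisor of every column. It does not. SAP 6 names an analysis set, and an at-risk count taken within the treated population would comply with it. This stands: all treated is the default reading, not a written rule.

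**The columns need not decline.** A reader might infer that late percentages will fall through dropout and suggest fading risk. The documents do not support that, because the last period is unbounded and its length can outweigh the dilution, as Step 4 shows. This also stands. What remains is understatement within each later period, and columns that cannot be compared.

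**Other outputs carry the information.** Counts sit beside percentages, TEAEs and treatment discontinuations are listed, and duration is summarised. With about 24 participants a determined reader could largely rebuild the risk sets. That limits the harm but does not correct the printed percentages. The trial is single-arm, the table is not among the interim analyses in SAP Table 2, and no decision rule uses it.

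**All treated is a legitimate denominator.** It answers what share of everyone treated had an onset in the period. The at-risk version answers a different question: it is conditional on remaining on treatment and leaves out those who stopped early for toxicity. With 10 to 12 at risk, one participant moves it by 8 to 10 points (1/12 = 8.3%, 1/10 = 10%). These are real limits, and they are reasons to print both the N and the counts.

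**Conclusion.** The concern holds as a gap in specification with a predictable effect on the default reading. The direction of that effect within a period follows from the arithmetic alone: once anyone has left the risk set, dividing by all treated understates the at-risk percentage. The pattern across periods cannot be predicted.

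The size cannot be derived from the documents, which give neither a discontinuation rate nor an expected time on treatment. The figure of 15% down to 8% for a true 20% rests on the assumed 75% to 40% at risk at week 32 and should be quoted only with that range.

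This is a minor, inexpensive improvement to one descriptive safety table. The test of ORR, its type 1 error and its power do not depend on it.

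**What to change.** Add to SAP 6.1, for the time-period table only:
- The percentage in each period uses as denominator the treated participants whose treatment-emergent window (first dose to last dose plus 30 days, cut at the data cutoff) reaches the start of that period.
- That N is printed in each column header.
- Events per 100 participant-months at risk are shown for every period, because the periods differ in length.
- The counts and the total column stay on all treated participants.

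A footnote should say that the period percentages are conditional on remaining on treatment and that the late denominators are small.

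The cost is one sentence or short list in the SAP and a changed layout for one table. The dosing and adverse event dates needed are already collected, and the safety analysis set stays as defined.
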